10.3.2. Vital Signs

Vital signs (blood pressure, heart rate, respiration, and axillary temperature) will be measured at the time points specified in [Table 2](#). Refer to the Study Manual for more details on the methods for obtaining vital signs.

For infusion visits, vital signs are to be collected within approximately 60 minutes prior to infusion and 30 minutes (\pm 10 minutes) after the end of the infusion. All assessments will be performed after patients have remained calm for 5 minutes. Pulse rate and respiratory rate should be measured over 1 minute.

10.3.3. Height/Length and Weight

Height/ulnar length and weight will be measured at the time points specified in [Table 2](#) prior to study drug infusions, to determine the volume of study drug to be administered. Details about how weight measurements are obtained are provided in the Study Manual. If a patient's weight or height/ulnar length varies by more than 10% from the corresponding assessment from the prior visit, the patient should be re-measured or re-weighed to confirm the result, and an explanation of the change should be documented.

Height will be measured at the time points specified in [Table 2](#). Height is to be measured with shoes off. If standing height cannot be obtained, height is to be calculated using the following equation ([Gauld 2004](#)):

$$\text{Height (cm)} = 4.605U + 1.308A + 28.003$$

where U is the length of the ulna in centimeters measured using an anthropometer or calipers, and A is the patient's age in years.

Ulnar measurements will be recorded for all patients at each site visit.

10.3.4. Safety Monitoring, Additional Investigations and Stopping Rules

10.3.4.1. Safety Monitoring for Liver Chemistry Tests

Liver chemistry tests need to be monitored as specified in the Schedule of Events ([Table 2](#)).

Initial abnormal liver chemistry test result(s) needs to be confirmed if:

- Gamma-glutamyl transferase (GGT) or Glutamate dehydrogenase (GLDH) or Aspartate aminotransferase (AST) or Alanine aminotransferase (ALT) measurement is $> 3 \times$ the upper limit of normal (ULN) (or $> 2 \times$ Baseline value if the Baseline value was $>$ ULN) at any time during the study.

Patients with confirmed liver chemistry test results (as above) need to have their liver chemistry tests (GGT, GLDH, ALT, AST, alkaline phosphatase), international normalized ratio [INR] and total bilirubin) retested 2 or 3 times weekly. Frequency of retesting can decrease to once a week or less if abnormalities stabilize or the trial drug has been discontinued and the subject is asymptomatic.

Additional Investigations:

Patients with confirmed abnormal liver chemistry test results (as above) are recommended to have the following evaluations performed:

- Obtaining a more detailed history of symptoms and prior or concurrent diseases.
- Obtaining a history of concomitant drug use (including nonprescription medications and herbal and dietary supplement preparations), alcohol use, recreational drug use, and special diets.
- Ruling out acute viral hepatitis types A, B, C, D, and E; autoimmune or alcoholic hepatitis; Non-Alcoholic SteatoHepatitis; hypoxic/ischemic hepatopathy; and biliary tract disease.
- Obtaining a history of exposure to environmental chemical agents.
- Additional liver evaluations, including gastroenterology/hepatology consultations, hepatic computed tomography (CT) or magnetic resonance imaging (MRI) scans, may be performed at the discretion of the Investigator, in consultation with the Sponsor Medical Monitor.

Stopping Rules for Liver Test Results:

In the event of laboratory results meeting the following criteria, **and the event is without an alternative explanation as discussed with the Sponsor Medical Monitor**, dosing of a patient with eteplirsen will be stopped permanently; values that are not confirmed due to failure to retest or missing lab values will be presumed confirmed:

- GGT or GLDH $> 8 \times$ ULN, which is confirmed
- GGT or GLDH $> 5 \times$ ULN, which is confirmed and persists for ≥ 2 weeks
- GGT or GLDH $> 3 \times$ ULN, which is confirmed **and** total bilirubin $> 2 \times$ ULN or INR > 1.5
- GGT or GLDH $> 3 \times$ ULN which is confirmed, and the new appearance (i.e., onset coincides with the changes in hepatic enzymes) of fatigue, nausea, vomiting, right upper quadrant pain or tenderness, fever, rash, or eosinophilia ($> 5\%$) felt by the Investigator to be potentially related to hepatic inflammation.

10.3.4.2. Safety Monitoring for Renal Function

Renal tests need to be monitored as specified in the Schedule of Events ([Table 2](#)). Patients with the following test results need to undergo repeat testing for confirmation of abnormal test results:

- Protein $\geq 2+$ (dipstick)
- Urine Protein to Creatinine Ratio $\geq 150\text{mg/g}$
- Urine Albumin to Creatinine Ratio $\geq 30\text{mg/g}$
- Serum Creatinine $\geq 0.3 \text{ mg/dL}$ above baseline
- Serum Creatinine $\geq 1.5 \times$ ULN
- Estimated glomerular filtration rate (eGFR) $\leq 60 \text{ ml/min}/1.73\text{m}^2$
- Red blood cells (RBCs) $> 1/\text{hpf}$
- Elevated Cystatin C $>$ ULN
- Elevated kidney injury molecule 1 $>$ ULN

Additional Investigations:

24-hour urine collection needs to be undertaken to quantify any proteinuria and glomerular filtration rate (GFR) changes indicated by confirmed results as above. Additional evaluations including nephrology consultation, renal US/CT/MRI, renal biopsy, may be performed at the discretion of the Investigator in consultation with the Sponsor Medical Monitor.

Stopping Rules for Renal Test Results:

In the event of laboratory results meeting the following criteria, **and the event is without an alternative explanation as discussed with the Sponsor Medical Monitor**, dosing of a patient with eteplirsen will be stopped permanently:

- Quantitative total urine protein measurement of $\geq 1 \text{ g}/24 \text{ hours}$
- Measured GFR (creatinine clearance) $\leq 45 \text{ mL/min}/1.73\text{m}^2$
- Gross hematuria
- Any RBC Casts
- Persistent microscopic hematuria $\geq 3 \text{ RBCs/hpf}$ for 3 consecutive weeks

10.3.4.3. Safety Monitoring for Hypersensitivity

Patients will be monitored for occurrence of allergic reactions primarily via monitoring adverse events as specified in the Schedule of Events ([Table 2](#)). Patients will be instructed to promptly report any signs or symptoms of fever or constitutional symptoms that may arise during the study and the Investigator needs to closely evaluate all potential causes, including concomitant illness.

Additional Investigations:

Patients who experience significant or persistent constitutional symptoms need to be discussed with the Sponsor Medical Monitor to determine whether additional monitoring or laboratory tests are required. Additional evaluations including immunology consultation, tests for allergic reactions (absolute eosinophils, serum/plasma tryptase), may be performed at the discretion of the Investigator in consultation with the Sponsor Medical Monitor.

Stopping Rules for Hypersensitivity AEs:

In the event of a confirmed hypersensitivity AE meeting the following criteria, **and the event is without an alternative explanation as discussed with the Sponsor Medical Monitor**, dosing of a patient with eteplirsen will have their treatment permanently discontinued.

- Anaphylaxis, anaphylactoid reaction, or angioedema
- Any serious allergic reaction

10.3.4.4. Safety Monitoring for Platelet Count Results

The platelet count needs to be monitored as specified in the Schedule of Events ([Table 2](#)).

Patients who have a confirmed occurrence of platelets < 75,000/ mm³ need to have the following evaluations performed:

- Complete blood count with reticulocytes
- Peripheral blood smear
- Coagulation panel (prothrombin time /INR, activated partial thromboplastin time)
- High-sensitivity C-reactive protein

Additional Investigations:

Additional platelet evaluations for confirmed, unexplained significant platelet count reductions, including hematology consultation, fibrinogen, fibrinogen split products/D-dimer, von Willebrand factor, total immunoglobulins, complement levels, viral serologies, auto-antibody screen, antiplatelet antibodies and anti-PF4 assay, may be performed at the discretion of the Investigator in consultation with the Sponsor Medical Monitor.

Stopping Rules for Platelet Test Results:

In the event of laboratory results meeting the following criteria, **and the event is without an alternative explanation as discussed with the Sponsor Medical Monitor**, dosing of a patient with eteplirsen will be stopped permanently:

- Platelet count < 50,000/mm³

Safety Monitoring for Rhabdomyolysis

Rhabdomyolysis must be monitored by urine dipstick and adverse events as specified in the Schedule of Events ([Table 2](#)).

- Patients who have confirmed heme+ dipstick urinalysis need to be evaluated for urine microscopy and the following AEs:
 - Rhabdomyolysis
 - Acute onset or exacerbation of Myalgia
 - Myoglobinuria
 - Chromaturia (e.g. tea-colored urine)

Additional Investigations:

In case of any of the adverse events above, subjects need to have evaluations of myoglobinuria, CK, renal function (eg, serum cystatin C) and serum chemistry two or three times weekly until values reach usual/pre-event levels or stabilize.

In addition, investigators should obtain a more detailed history of symptoms, preceding activity and hydration status, concomitant drug use, and recent or concurrent infections. Additional evaluations, including rheumatology/immunology consultations and anti-muscle antibodies, may be performed at the discretion of the Investigator in consultation with the Sponsor Medical Monitor.

10.3.5. Clinical Safety Laboratory Evaluations

The following routine clinical safety laboratory tests will be collected at the time points specified in [Table 2](#), samples prepared according to the Laboratory Manual provided for the study, and results analyzed by an accredited central laboratory selected by the Sponsor:

Chemistry: Sodium, chloride, potassium, calcium, glucose, creatinine, blood urea nitrogen, albumin, uric acid, total bilirubin, alkaline phosphatase, amylase, alanine aminotransferase, aspartate aminotransferase, GGT, GLDH, C-reactive protein, creatine kinase (CK), and serum cystatin C

Hematology: Complete blood count with differential

Coagulation Screen: Prothrombin time, International Normalized Ratio, and activated partial thromboplastin time

Persistent, unexplained abnormalities on routine renal blood test monitoring will result in additional renal function tests such as eGFR and 24-hour urine testing for protein.

A description of blood volumes to be drawn is provided in Section 17.1.

Any value outside of the current reference ranges for the laboratory performing the test will be flagged on the laboratory results. The Investigator will determine whether abnormal assessment

results are clinically significant or not. Clinical significance is defined as any variation in assessment results that has medical relevance resulting in an alteration in medical care. If clinically significant deterioration from Baseline levels is noted, the Investigator will continue to monitor the patient with additional assessments until:

- Values have reached normal range and/or Baseline levels, or
- In the judgment of the Investigator together with the Sponsor Medical Monitor, abnormal values are assessed to be not related to the administration of IP or other protocol-specific procedures, and additional assessments are not medically indicated.

10.3.5.1. Laboratory Assessments of Interest

The review of the DMC will include evaluation of laboratory assessments of interest, which include:

- Any moderate or serious event without an alternative etiology that the Investigator deems is related to study drug
- Two consecutive, study drug-related serum creatinine levels $\geq 2 \times$ ULN, without an alternative etiology.
- CK levels $> 50,000$ U/L
- A confirmed, unexplained increase in GGT or GLDH $> 3 \times$ ULN and either an increase in bilirubin $> 2 \times$ ULN or nascent prothrombin time $> 2 \times$ ULN, concurrently, without an alternative etiology

10.3.6. Electrocardiogram

Twelve-lead ECGs will be obtained at the time points specified in [Table 2](#). ECGs will be performed at a consistent time of day throughout the study, but before performing any invasive procedures (ie, blood sampling or study drug infusions). ECGs should be performed by trained staff after the patient is in the supine position, resting, and quiet, when possible. ECG findings will be manually reviewed and interpreted by medically qualified personnel, using a central vendor, according to prespecified criteria. The Investigator will review the results of the centrally-read ECG report and determine if the findings are clinically significant.

Clinical significance is defined as any variation in ECG findings that has medical relevance resulting in an alteration in medical care. If clinically significant worsening from Baseline is noted, the Investigator will continue to monitor the patient with additional assessments until:

- Findings have returned to normal and/or Baseline levels, or
- In the judgment of the Investigator together with the Sponsor Medical Monitor, abnormal findings are assessed to be not related to the administration of IP or other protocol-specific procedures, and additional assessments are not medically indicated.

10.3.7. Concomitant Medications and Therapies

Concomitant medications, changes in the dosage of concomitant medications, and concomitant therapies will be reviewed and recorded at each visit from the time the patient and/or parent/legal guardian provides signed informed consent. Information on any physiotherapeutic interventions

must be collected in detail for this study. See Section 9.4 for details on permitted concomitant medications.

10.3.8. Adverse Events

AEs will be monitored throughout the study, from signing of the informed consent form through each patient's Safety Follow-up visit, which will occur approximately 4 weeks after the last eteplirsen infusion, regardless of the patient's duration in the study.

10.4. Pharmacokinetic Assessments

Not applicable.

10.5. Exploratory Assessment

10.5.1. CCI Scale

The CCI is to be performed by qualified, trained staff.

The CCI is a clinician-administered scale that rates patient performance on various functional activities ([Mazzone 2011](#)). It was designed to be used in boys with DMD who are able to stand, and has been used in young boys with DMD ([Connolly 2013](#), [Mercuri 2016](#)). During this assessment, patients perform 17 different functional activities, including a 10-meter walk/run, rising from a sit to stand, standing on one leg, climbing a box step, descending a box step, rising from lying to sitting, rising from the floor, lifting the head, standing on heels, and jumping.

Patients will be graded as follows: 2 = normal, no obvious modification of activity; 1 = modified method but achieves goal independent of physical assistance from another; and 0 = unable to achieve goal independently. Patients will only undergo testing of additional items that have not already been assessed before (eg, "standing on heels"), to allow for calculation of the CCI.

Details on administration of the additional CCI test items are provided in the Clinical Evaluator Manual.

11. ADVERSE EVENTS

11.1. Collection of Adverse Events

Over the entire duration of the study, study site personnel will ensure that all AEs are recorded appropriately. If an AE occurs, the primary concern is for patient safety, and the Investigator will use professional judgment and expertise to determine the appropriate course of action.

All AEs from the time of signed informed consent through the Safety Follow-up visit (which will occur approximately 4 weeks after the last infusion of eteplirsen, regardless of the patient's duration in the study) will be recorded in each individual patient's electronic case report form (eCRF). If at any time after the patient has completed participation in the study, the Investigator or study staff becomes aware of a SAE that the Investigator believes is related to the IP (Section 11.3.1) or is related to a study procedure (Section 11.3.2), then the event and any known details must be reported promptly to the Sponsor.

11.2. Definition of Adverse Events

11.2.1. Adverse Event

An AE is any untoward medical occurrence in a clinical trial participant, which does not necessarily have a causal relationship with the investigational drug. An AE can, therefore, be any unfavorable and unintended symptom, sign, disease, condition, or test abnormality that occurs during or after administration of an IP, whether or not considered related to the IP.

Adverse events include:

- Symptoms described by the patient or signs observed by the Investigator or medical staff
- Test abnormalities (eg, laboratory tests, ECG, X-rays, etc.) that result in an alteration in medical care (diagnostic or therapeutic)

Abnormalities present at Baseline are considered AEs only if they re-occur after resolution or worsen during the AE collection period.

An AE will be defined as a treatment-emergent adverse event (TEAE) if it developed or worsened in the period from the first dose of study drug to 28 days after the last dose of study drug.

11.2.2. Serious Adverse Event

An SAE is defined as any AE that results in any of the following:

- **Death:** The patient died as the result of the event.
- **Life-threatening event:** Any AE that places the patient, in the view of the Investigator or Sponsor, at immediate risk of death from the AE as it occurred ie, does not include an AE that had it occurred in a more severe form, might have caused death.
- **Required or prolonged inpatient hospitalization:** The AE resulted in hospitalization or prolonged an existing hospitalization. Since hospitalization may be

part of the study, only hospitalizations that are longer than expected, based on Investigator judgment, will be considered prolonged hospitalizations.

- **Persistent or significant disability/incapacity:** An AE that results in a substantial disruption of a person's ability to conduct normal life functions.
- **Congenital anomaly/birth defect:** A congenital anomaly/birth defect that occurs in the offspring of a patient exposed to the IP.
- **Important medical event:** An AE that may not result in death, be life-threatening, or require hospitalization may be considered an SAE when, based upon appropriate medical judgment, the event may jeopardize the patient and may require medical or surgical intervention to prevent one of the outcomes listed above.

11.3. Classification of Adverse Events

Each AE, whether serious or nonserious, will be classified by the Investigator according to the following rules and definitions.

11.3.1. Relationship to Investigational Product

For each AE, the Investigator will determine whether there is a reasonable likelihood that the AE may have been caused by the study treatment, according to the categories below:

Unrelated: There is no reasonable possibility that the event is related to the investigational drug product.

Related: There is a reasonable possibility that the event is related to the investigational drug product.

Adverse events that the Investigator or Sponsor considers to be related to the IP will be considered adverse drug reactions.

A treatment-related TEAE will be defined as a TEAE that the Investigator considers related to the study treatment.

11.3.2. Relationship to Study Procedures

For each AE, the Investigator will determine whether there is a reasonable possibility that the AE may have been caused by the study procedures, according to the categories below:

Unrelated: There is no reasonable possibility that the event is related to the study procedures.

Related: There is a reasonable possibility that the event is related to the study procedures.

11.3.3. Relationship to Underlying Disease

For each AE, the Investigator will determine whether there is a reasonable possibility that the AE may be related to the underlying disease, according to the categories below:

Unrelated: There is no reasonable possibility that the event is related to the underlying disease.

Related: There is a reasonable possibility that the event is related to the underlying disease.

Events of disease progression may be considered AEs, based on the Investigator's discretion.

11.3.4. Severity of Adverse Events

Note that severity is not the same as "seriousness," which is defined in Section 11.2.2 and which serves as a guide for defining regulatory reporting obligations.

The Investigator will assess the severity of all AEs as mild, moderate, or severe, based on the following definitions:

Mild: The event does not interfere with the patient's usual activities.

Moderate: The event interferes with the patient's usual activities.

Severe: The event prevents the patient from undertaking their usual activities and requires therapeutic intervention or cessation of the IP.

11.3.5. Outcome

Outcome describes the status of the AE. The Investigator will provide information regarding the patient outcome of each AE in the eCRF.

11.3.6. Action Taken Regarding the Investigational Drug Product

The Investigator will provide information regarding the action taken with respect to the IP in response to the AE in the eCRF.

11.3.7. Expectedness of an Adverse Event

The expectedness of all AEs will be determined according to the most recent version of the eteplirsen Investigator's Brochure.

11.3.8. Suspected Unexpected Serious Adverse Reactions

Suspected unexpected serious adverse reactions (SUSARs) will be handled by appropriate personnel at the Sponsor or designee, and reported within the required timelines in an unblinded fashion to regulatory authorities and the IRBs/IECs, per the requirements of the concerned competent bodies. All SUSARs will also be reported to study Investigators.

11.3.9. Adverse Events of Special Interest

Adverse events of special interest are AEs (serious or nonserious) that are of special scientific and/or medical interest, for which ongoing and rapid communication by the Investigator to the sponsor is appropriate.

The AESIs for this study are listed below. All AESIs should be reported as AEs to the sponsor within 24 hours of awareness irrespective of adverse event seriousness. This includes the events below that are based on lab abnormalities, which should be translated to an appropriate adverse event term at the time of reporting.

Nephrotoxicity

- Proteinuria $> 500 \text{ mg/24 hr}$
- eGFR $< 60 \text{ ml/min/1.73 m}^2$

Hepatotoxicity

- GGT or GLDH $> 8 \times \text{ULN}$
- GGT or GLDH $> 5 \times \text{ULN}$ for more than 2 weeks
- GGT or GLDH $> 3 \times \text{ULN}$ and (total bilirubin $> 2 \times \text{ULN}$ or international normalized ratio > 1.5)
- GGT or GLDH $> 3 \times \text{ULN}$ with the appearance of the following signs or symptoms: fatigue, vomiting, right upper quadrant pain or tenderness, fever, rash, and/or eosinophilia ($> 5\%$)

Hypersensitivity

- Anaphylaxis, anaphylactoid reaction, or angioedema
- Any severe allergic reaction
- Any severe complement mediated, inflammation event (eg, acute kidney injury, arteritis, myocarditis, pneumonitis)

Thrombocytopenia

- Platelet count $< 75,000/\text{mm}^3$

Infusion-related reactions

- All infusion related reactions considered severe (see Section 11.3.4), occurring within 24 hours of the eteplirsen infusion, should be reported to the Sponsor within 24 hours of awareness.

Infusion-related reactions may include headache, vomiting, diarrhoea, pyrexia, abdominal pain, upper, flushing and nausea. There may be pain at the site of the infusion as well as bruising surrounding the infusion site. Infections are also possible at the site of the infusion.

Rhabdomyolysis

- Rhabdomyolysis adverse events regardless of severity

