NAME OF ACTIVE INGREDIENT	Eteplirsen

INCLUSION/EXCLUSION CRITERIA:

Inclusion Criteria:

A patient must meet all of the following criteria to be eligible to participate in this study:

1. Patient has successfully completed 96 weeks of treatment in Study 4658-102.
2. Parent(s) or legal guardian(s) who is/are able to understand and comply with the study requirements.
3. Patient and/or their parent(s)/legal guardian(s) are willing and able to provide signed informed consent.

Exclusion Criteria

A patient who meets the following criterion will be excluded from this study:

1. Patient has a prior or ongoing medical condition that, in the Investigator's opinion, could adversely affect the safety of the patient, or make it unlikely that the course of treatment or follow-up would be completed, or impair the assessment of study results.

DOSE/ROUTE/REGIMEN(TEST ARTICLE):

The dose of eteplirsen will be calculated based on the most recent patient weight obtained at the site prior to the current visit. Please refer to the study-specific Pharmacy Manual for information on preparation and administration of eteplirsen.

Patients will receive the **cc** mg/kg dose of eteplirsen for up to 284 weeks while in the study.

CCI

It is recommended that a topical anesthetic cream (eg, lidocaine 2.5%, prilocaine 2.5%, or LMX4 cream) be applied to the infusion site prior to each administration of study drug. Patients should be observed for possible reactions to the infusion for at least 1 hour after each infusion. Home infusion of the study drug may be available.

NAME OF COMPANY Sarepta Therapeutics, Inc. [name] [contact]	NAME OF FINISHED PRODUCT Eteplirsen Injection
	NAME OF ACTIVE INGREDIENT Eteplirsen
REFERENCE TREATMENT: None	
CRITERIA FOR EVALUATION:	
Safety and Tolerability The safety and tolerability of eteplirsen will be assessed through a review and evaluation of: 
• The frequency and severity of AEs, serious adverse events (SAEs), and discontinuation of treatment due to AEs• Deaths due to AEs• Adverse events of special interest, including infusion-related reactions, hypersensitivity, and renal events• Laboratory testing, including hematology, coagulation, serum chemistry, and urinalysis• Cardiac function assessments, including electrocardiogram (ECG)• Vital signs• Physical examinations	

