5.5. Benefit and Risk Assessment

Details about the known and expected benefits and risks of, and expected AEs associated with, eteplirsen treatment are provided in the eteplirsen Investigator's Brochure.

Eteplirsen has been granted accelerated approval in the US by the Food and Drug Administration. This was based on the observation of dystrophin production in some patients and the safety experience in patients with DMD participating in clinical trials, who were 4 years of age or older, which includes the age range specified for this study. Patients have also used commercially available eteplirsen since the approval in September 2016.

To date, eteplirsen has been well tolerated, with low rates of serious or severe AEs. No major safety risk has been identified in patients dosed with eteplirsen, including patients dosed with up to 50 mg/kg once weekly for more than 4 years.

Risks with eteplirsen include infusion-related reactions, hypersensitivity reactions, and potential renal toxicities including proteinuria or decreased renal function. These events have been seen in prior experience with eteplirsen with lower doses and are usually mild and resolve without clinical or pharmaceutical treatment. The use of higher doses of eteplirsen in this protocol could lead to more frequent or more severe reactions than seen with lower doses. Regularly scheduled review by a Safety Review Committee during the open-label period and a Data Monitoring Committee (DMC) during the double-blind period will look at aggregate unblinded data to determine the relative risk-benefit of continuing the dose or the study. Investigators are allowed to withhold dosing and must discuss such actions with the Medical Monitor. Further details on the safety of eteplirsen can be found in the Investigator's Brochure.

Based on the mechanism of action of eteplirsen and the benefit of eteplirsen treatment in DMD patients with mutations amenable to skipping exon 51, it is expected that patients in Study 4658-102-OLE may derive a clinical benefit from treatment with a higher dose of eteplirsen.

Taken together, these considerations support that patients participating in Study 4658-102-OLE will not be exposed to undue risk and may potentially experience some clinical benefit.

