7.3. Study Endpoints

7.3.1. Safety and Tolerability Endpoints

- Incidence of AEs, serious adverse events (SAEs), and discontinuation from treatment due to AEs
- Incidence of deaths due to AEs
- Incidence of adverse events of special interest (AESIs), including infusion-related reactions, hypersensitivity, and renal events
- Clinically significant laboratory testing, including hematology, coagulation, serum chemistry, and urinalysis
- Clinically significant cardiac function assessments, including electrocardiogram (ECG)
- Clinically significant vital signs
- Clinically significant physical examinations

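### Three of the five renal findings that permanently stop dosing are not named in the AESI list, so an isolated case need not enter the AESI incidence endpoint

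*Combined protocol and SAP*

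**What the plan says.** Safety and tolerability is the primary objective (Section 6.1). Section 7.3.1 makes one of the endpoints "Incidence of adverse events of special interest (AESIs), including infusion-related reactions, hypersensitivity, and renal events", and the synopsis repeats it as "Adverse events of special interest, including infusion-related reactions, hypersensitivity, and renal events". Section 13.7.1 gives AESIs their own table and listing.

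The only definition of an AESI is in Section 11.3.9: "The AESIs for this study are listed below". Nephrotoxicity has two lines there, proteinuria above 500 mg/24 hr and eGFR below 60 ml/min/1.73 m². Every AESI must reach the sponsor within 24 hours of awareness, whether or not it is serious.

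Section 10.3.4.2 sets the renal stopping rules. If no other cause is found after discussion with the Medical Monitor, "dosing of a patient with eteplirsen will be stopped permanently" for any of five findings. Two concern urine protein and measured GFR. The other three are "Gross hematuria", any RBC casts, and "Persistent microscopic hematuria" (at least 3 RBCs/hpf for 3 consecutive weeks).

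Section 5.5 lists among the known risks "potential renal toxicities including proteinuria or decreased renal function".

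**The concern.** The AESI endpoint is expected to show renal events, and a permanent stop is the strongest action the protocol takes for one child. A reader of the AESI table would expect a child stopped under a renal rule to be in it. For three of the five rules the list in Section 11.3.9 does not put him there. With at most 15 children, one case decides whether a row reads zero. The 24-hour AESI report is also not triggered for these findings. A 24-hour report would then depend on the event being serious (Section 11.5).

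**Working it through.** The plan has no figure to reproduce: Section 13.3 states no formal sample size calculation. The check is a mapping of the stopping rules onto the AESI lines, followed by simple arithmetic.

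**Step 1. Renal rules (10.3.4.2) against AESI lines (11.3.9).**

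| Permanent-stopping finding | AESI line | Match |
|---|---|---|
| Urine protein ≥ 1 g/24 h | Proteinuria > 500 mg/24 hr | Covered (1,000 > 500) |
| Measured GFR ≤ 45 | eGFR < 60 | Close, but measured against estimated |
| Gross hematuria | none | Absent |
| Any RBC casts | none | Absent |
| ≥ 3 RBCs/hpf for 3 consecutive weeks | none | Absent |

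Two of five have a line and three do not. No other AESI heading names hematuria or casts.

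**Step 2. Is this the protocol's general pattern?** Section 10.3.4 has 4 liver + 5 renal + 2 hypersensitivity + 1 platelet = 12 permanent-stopping criteria.

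- Fully covered, 5: GGT or GLDH > 8 × ULN; > 3 × ULN with bilirubin or INR; urine protein; the anaphylaxis group; platelets (stop below 50,000, AESI below 75,000).
- Covered on a different measure, 1: GFR.
- Line present with a wording difference, 3: the liver duration (at least 2 weeks against more than 2 weeks); the liver symptom list (nausea appears only in the stopping rule); allergic reactions (serious in the stopping rule, severe in the AESI list).
- Absent, 3: the hematuria and cast findings.

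5 + 1 + 3 + 3 = 12. By domain, criteria with some AESI line are liver 4 of 4, hypersensitivity 2 of 2, platelets 1 of 1 and renal 2 of 5. All three absences are renal.

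**Step 3. Which children are affected?** Other rules catch many of them. Section 10.3.4.2 says "24-hour urine collection needs to be undertaken to quantify any proteinuria and glomerular filtration rate (GFR) changes indicated by confirmed results as above", so accompanying proteinuria above 500 mg/24 hr would be found and would be an AESI. A confirmed heme-positive dipstick leads to microscopy and evaluation for rhabdomyolysis (10.3.4.4), which is an AESI at any severity. A severe complement-mediated event is also an AESI. What remains is isolated hematuria or casts: protein no higher than 500 mg/24 hr, eGFR not below 60, no rhabdomyolysis and no severe complement-mediated event.

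**Step 4. Size of one omission.** Input: n = 15, the maximum in Section 8.1. For one such child with no other AESI during the study, the change is 1/n:

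- n = 15: 1/15 = 6.7 percentage points.
- n = 12 (assumed): 1/12 = 8.3 points.
- n = 10 (assumed): 1/10 = 10 points.

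As an illustration, suppose there are no other AESIs at n = 15. Exact (Clopper-Pearson) 95% limits are:

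- 0/15: 0% to 1 − 0.025^(1/15) = 21.8%.
- 1/15: 1 − 0.975^(1/15) = 0.2%, to the 97.5% point of Beta(2, 14) = 31.9%.

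The table would read 0% (0 to 21.8%) instead of 6.7% (0.2 to 31.9%). The documents give no probability for these findings, so no expected count can be stated.

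**The case against.** The strongest reply is that AESIs and stopping rules serve different purposes. Nothing in the protocol requires every stopping criterion to be an AESI. Section 11.3.9 ties AESIs to rapid communication with the sponsor, and the two renal lines match the two examples in Section 5.5. That communication largely happens anyway: a permanent stop involves discussion with the Medical Monitor (10.3.4.2), and Section 9.6 requires immediate notice to the study monitor and DMC review.

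Nor is the child lost to the safety analysis. A test abnormality that changes care is an AE (11.2.1), so a finding that stops dosing appears in the TEAE table and in the table of AEs leading to treatment discontinuation (13.7.1). Urinalysis is summarized (13.7.2), and all safety data are listed (13.7). A reader might infer that a renal stop could go unseen; the documents do not support that.

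A reader might also infer that such a child is certain to be missing from the AESI count. That too is more than the text allows. Section 7.3.1 speaks of renal events without defining them, Section 13.1 defers the methods to a SAP, and the SAP text is not supplied. It could regroup these events.

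These replies limit the consequence, but they do not supply an AESI line. The list in 11.3.9 has no wording that leaves it open, and the examples in 5.5 are introduced as examples. A SAP can regroup events for analysis, but it is not where the site's 24-hour AESI duty is set.

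**Conclusion.** The point holds as a minor one. The only AESI definition in the documents omits three of five renal permanent-stopping findings, while all nine other stopping criteria have a matching or near-matching line. As written, a child stopped for isolated hematuria or casts need not enter the AESI incidence endpoint, and the 24-hour AESI report does not apply. The consequence is confined to that table and that reporting route.

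The 6.7 points rest on three assumptions: full enrolment of 15, one affected child with no other AESI, and no regrouping in the SAP. The figure is the effect of a case if one occurs, not a forecast that one will.

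**What to change.** Add three objective lines under Nephrotoxicity in Section 11.3.9: gross hematuria; any RBC casts; and confirmed microscopic hematuria of at least 3 RBCs/hpf for 3 consecutive weeks. Make them reportable within 24 hours of awareness, without waiting for the judgement on other causes. This keeps them like the existing laboratory-based lines, with a clear start to the reporting clock. Count them as renal events in the AESI table. The stopping rules stay as they are.

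Optionally, align the three near-matches: add nausea to the liver symptoms, change the duration to at least 2 weeks, and refer to serious or severe allergic reactions.

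Cost: no new tests are needed. The reported AESI rate may be slightly higher and may include some hematuria with another cause, and there will be a few more 24-hour reports. The wording needs a protocol amendment, which Section 14.2 subjects to IRB/IEC and regulatory authority review, so it is best carried in an amendment made for other reasons.
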